### **B.6.1. Pilot Study # 1: Promoting physical activity (PA) among breast cancer survivors in Colombia**

**Rationale:** Breast cancer is the most common cancer in women worldwide. In Colombia, nearly 5,000 new cases are diagnosed annually. PA is associated with decreased cancer risk. A growing body of evidence supports the idea that increasing PA provides important benefits to psychological and physical wellbeing in breast cancer patients. We will design a theory-based intervention to integrate PA promotion into clinical care for breast cancer survivors, with the ultimate goal of secondary prevention and enhanced survival.

**Methods:** We will conduct a small, randomized controlled study of a PA intervention among 60 breast cancer patients (18-65 years). Eligible women will be randomized to the PA intervention or a control group that will receive an education program not related to PA. The intervention will include supervised exercise through dancing and a culturally relevant and piloted smartphone app aimed at promoting PA and decreasing sedentary behavior. The primary outcomes for this pilot will be weekly minutes of PA, quality of life, and mental health – specifically, anxiety and depression. This project will involve partnerships between researchers at Stanford School of Medicine, the Institute of Sports and Recreation in Bogotá, the Universidad del Rosario, the Foundation Simmon, the National Cancer Institute of Colombia, and UniAndes.

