**Analysis:** We will use a mixed methods approach to assess acceptability, feasibility, and preliminary effectiveness of the intervention. **Acceptability/feasibility:** Qualitative methods will include focus group discussions with participants at the conclusion of the study to explore acceptability and feasibility. Non-participants will be included in focus groups to examine factors influencing participation. Quantitative methods will include ratings of intervention components to capture acceptability, practicality, and motivational capabilities on a Likert-type 7-point scale (with a goal of obtaining acceptability mean ratings  $\geq 6$  out of 7). **Preliminary effectiveness:** To assess preliminary effectiveness, we will use repeated measures ANOVA, Kruskal–Wallis and McNemar tests to establish the change in outcomes before and after treatment. Outcomes will include physical activity/sedentary behavior, health-related quality of life, and anxiety and depression. (All measures have been tested in and shown to be appropriate for Latino populations.)

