Evidence-based strategies to promote physical activity encompass approaches that target individuals, their families, the neighborhoods in which they live, work, and play, and the policies that shape their opportunities for leading active lives. Additionally, physical activity interventions are easily culturally targeted and tailored, especially when community-based participatory research approaches are employed, making them an ideal approach for reducing NCD risk in regions such as Latin America with rich and heterogeneous cultural backgrounds. To support such potentially effective approaches, significant investment in the research capacity in the region is needed. Currently, in Colombia and the Latin American region, research has focused largely on observational methods for physical activity surveillance and examination of multi-level determinants of physical activity levels (e.g., individual, family, and neighborhood). With this critically important information on activity levels and determinants, the region now has an opportunity to build upon this foundation to create a body of research focused on behavior change through multiple levels of influence. The plans for research studies, research enhancement, and shared core facilities will be informed by the mixed methods needs assessment as described in the Coordinating Unit.

The Specific Aims of the Planning Unit are the following:

**1. Complete two pilot studies of physical activity interventions that focus on distinct levels of influence in diverse populations.** One pilot study will use a randomized controlled trial design to examine the preliminary effectiveness of a physical activity intervention for breast cancer patients. A second pilot study will use a longitudinal cohort design of Ciclovías and Recreovías in Colombia.

**2. Take advantage of Stanford's expertise in core research areas to train world leaders in behavioral science research at Universidad de los Andes to support regional expertise in physical activity intervention research.** A multi-pronged educational approach is planned for increasing research capacity among research partners, students, and community members. Activities will include developing a masters of science degree, a professional certificate program, and mini-courses for key stakeholders.

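### Pilot Study 1 plans repeated-measures ANOVA on before/after change; a baseline-adjusted comparison of the arms is more precise and avoids bias from dropout that depends on baseline

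*Combined protocol and SAP*

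**What the plan says.** Combined protocol and SAP, section B.6.1, Methods: "Eligible women will be randomized to the PA intervention or a control group". The total is 60. "The primary outcomes for this pilot will be weekly minutes of PA, quality of life, and mental health", the last specified as anxiety and depression. The Planning Unit aims describe this as a randomised design to "examine the preliminary effectiveness of a physical activity intervention for breast cancer patients".

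The effectiveness analysis is one sentence under Analysis in the same section: "we will use repeated measures ANOVA", then Kruskal–Wallis and McNemar "tests to establish the change in outcomes before and after treatment". It does not say which test goes with which outcome. It names no arm term, no arm-by-time interaction and no adjustment for baseline. The only timing given is "before and after treatment", so the text supports one measurement at each end.

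The documents state no analysis set, missing-data method, expected dropout, or rule for measuring women who stop. Retention appears only as a general task of the Coordinating Unit (its section B.2). No outcome is defined as binary.

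**The concern.** Two features of the named method matter in a trial this small.

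- **Precision.** With two time points, the only part of a repeated-measures ANOVA that compares the arms is the arm-by-time term, and this equals the difference in mean raw change. Raw change subtracts the whole baseline value, although baseline predicts follow-up only in part, and so adds noise that adjustment avoids.
- **Dropout.** In its classical form the method uses only women with both measurements. One arm is asked to do supervised exercise and the other attends unrelated education, so dropout could well differ between arms. If it also depends on baseline, the remaining women differ at baseline between arms, and raw change carries regression to the mean into the estimated effect.

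McNemar has a different limitation. It tests paired change within a group and yields no contrast between arms.

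At stake is the effect estimate that the pilot would pass on to the larger studies it is meant to inform (Planning Unit, section B.1.4).

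**Working it through.** **Inputs from the documents.** Two randomised arms, 60 women, one measurement before and one after. The figure of 60 cannot be reproduced, because no alpha, power, effect size, SD or dropout is given.

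**Assumed inputs.** 30 per arm, two-sided 5% test, outcome SD 1, true effect 0.5 SD, normal outcomes, baseline/follow-up correlation ρ of 0.5 (range 0.3 to 0.7), dropout 30% in the intervention arm and 10% in control. Follow-up data then exist for 21 and 27 women, 48 in all.

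**Step 1: precision when dropout is random.** The per-woman variance is 2(1 − ρ) for raw change and 1 − ρ² for ANCOVA. The ratio is 2/(1 + ρ).

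| ρ | Raw change | ANCOVA | Ratio |
|---|---|---|---|
| 0.3 | 1.40 | 0.91 | 1.54 |
| 0.5 | 1.00 | 0.75 | 1.33 |
| 0.7 | 0.60 | 0.51 | 1.18 |

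At ρ = 0.5, 1/21 + 1/27 = 0.0847.
- Raw change: SE = √(1.00 × 0.0847) = 0.291; power ≈ Φ(0.5/0.291 − 1.96) = Φ(−0.24) = 0.40.
- ANCOVA: SE = √(0.75 × 0.0847) = 0.252; power ≈ Φ(0.5/0.252 − 1.96) = Φ(0.02) = 0.51.

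Simulation with t-tests gives about 39% and 49%, with no bias in either. With 10% random dropout in both arms the figures are 43% and 55%.

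**Step 2: dropout that depends on baseline.** Let D be the baseline difference, intervention minus control, among women with both measurements. If dropout depends only on baseline, raw change estimates the true effect minus (1 − ρ)D, and ANCOVA estimates the true effect.

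Simulation used 6,000 trials per scenario, with intervention dropout logistic in baseline (slope −1.5 per SD, mean 30%) and control dropout random at 10%.

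| ρ | Raw-change ANOVA | Baseline-adjusted |
|---|---|---|
| 0.3 | 0.27 to 0.28 | 0.50 |
| 0.5 | 0.34 | 0.50 |
| 0.7 | 0.40 | 0.50 |

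The formula agrees. At ρ = 0.5 the bias is 0.34 − 0.50 = −0.16, so D = 0.16/0.5 = 0.32. It then predicts 0.50 − 0.7 × 0.32 = 0.28 at ρ = 0.3 and 0.50 − 0.3 × 0.32 = 0.40 at ρ = 0.7. At ρ = 0.5 power is about 21% against 47%. With no true effect, the ANOVA rejects in 7 to 10% of trials, against about 5%.

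The result depends on the mechanism (all at ρ = 0.5): 0.375 SD at slope −1.0, 0.42 at slope −0.5, 0.38 with 20% dropout at slope −1.5, and 0.50 (no bias) when both arms lose 20% by the same mechanism. A separate large-sample calculation, with dropout depending on baseline in both arms at 30% and 10%, gives D = 0.213. The formula predicts −0.5 × 0.213 = −0.107; the simulated bias was −0.105.

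**Step 3: dropout that depends on what is not observed.** With the same rates, ρ = 0.5, and intervention dropout depending on the follow-up value (slope −1.5), the ANOVA gives about 0.66 SD and ANCOVA 0.75 SD. With no true effect they reject in about 9% and 16% of trials. In the large-sample calculation, where dropout in both arms depends on a woman's own change, the biases are +0.21 (ANOVA) and +0.17 (likelihood analysis). Over correlations of 0.3 to 0.7 and intervention dropout of 20 to 40%, with 10% in control, the ANOVA bias runs from −0.22 to +0.38 SD across the selective mechanisms.

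**The case against.** The strongest reply is that the plan says nothing about dropping women. It contains no written completer rule and no dropout figure, and some software fits what it calls repeated-measures ANOVA as a mixed model that keeps incomplete cases. That stands. A reader might infer that the plan commits to completers only, and that dropout from the exercise arm will bias the effect. The documents support neither statement as fact. Random dropout, however unequal, costs only precision, and the same selective mechanism at equal rates in both arms gave no bias.

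A second reply is that the remedy does not bring back the women who leave. That also stands. With one follow-up, a baseline-constrained mixed model reduces to ANCOVA, and its contrast rests on the same roughly 48 women. The gain comes from conditioning on baseline, so it would be wrong to say that the change restores the comparison of all women randomised.

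Third, adjustment can do worse than the ANOVA when dropout depends on the follow-up value (Step 3). This is as plausible as dropout by low-baseline women, and it is why a sensitivity analysis belongs in the fix.

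Fourth, the power contrast of 21% against 47% overstates the part due to dropout. With random dropout the gap is already 39% against 49%, so about 10 of the 26 points are ordinary precision.

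Finally, this is a small pilot, and the text names neither an arm-by-time term nor a binary outcome. Kruskal–Wallis can compare independent groups, so a comparison of arms may be intended. But the sentence describes only before/after change, and no reply gives a reason to prefer raw change to a baseline-adjusted contrast.

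**Conclusion.** The point holds as a free improvement in method with a conditional bias argument attached. The gain in precision needs no assumption about selective dropout: raw change has 1.18 to 1.54 times the variance of ANCOVA for correlations of 0.7 down to 0.3, and at 0.5 power rises by about 10 percentage points. The bias is a risk, not a documented fact. It needs dropout that depends on baseline and differs by arm; under the strong mechanism assumed here it reduces 0.50 SD to about 0.34 SD, and less under weaker ones. Adjustment removes that bias only. Under other mechanisms the sign can reverse, and adjustment can be better or worse than the ANOVA.

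Every number except the total of 60 rests on assumed allocation, effect size, correlation, dropout and normality.

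**What to change.** In section B.6.1, Analysis:

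- Make the primary analysis of each continuous outcome a between-arm comparison at follow-up, adjusted for that outcome's baseline value (ANCOVA). If there is more than one follow-up, use a linear mixed model on all randomised women with any measurement, with visit, arm-by-visit, a common baseline mean and unstructured covariance.
- Report the arm difference with its 95% CI, and dropout by arm.
- If an outcome is dichotomised, compare the arms by logistic regression adjusted for baseline status instead of McNemar.
- Add a sensitivity analysis for dropout that depends on the unobserved follow-up value, for example by shifting the assumed outcomes of missing women over a stated range, separately by arm.

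The cost is a few lines of SAP text and standard procedures. It needs no further women and no further measurements.

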### **B.6.2. Evaluation of community Ciclovía/Recreovía programs to promote PA in public spaces**

**Rationale:** The Ciclovía is a multi-sector program in which streets are closed to motorized vehicles and open exclusively for individuals to enjoy safe, free spaces for leisure activities. Ciclovías at least twice/year are implemented in at least 496 cities in 27 countries, and 93% of programs are in Latin America. The model for many of them worldwide is the Bogotá Ciclovía. The Recreovía is a community-based PA program that comprises free PA classes in public spaces (parks, plazas, streets, malls, community centers) led by trained instructors. In 2015, Recreovía offered PA classes in 41 hubs in 95% of Bogotá's districts, with 75% of those hubs in low- to middle-income neighborhoods. We will design the prospective evaluation of the Ciclovía/Recreovía programs to promote PA and cancer prevention among women (ultimate goal=primary prevention).

**Methods:** We will: 1) design and develop the logic model/ theory-based instruments for these existing programs that promote PA in public spaces; 2) assemble, based on previous cross-sectional studies, an appropriate cohort study including 100 adults  $\geq 30$  years old who are regular users of the programs (i.e., participate every week) and irregular users of the program (i.e., once a month or less) with a follow-up after 6 months; 3) measure initial uptake of the program and demonstrate the feasibility of follow-up over time. This project will involve partnerships between Stanford researchers, the Institute of Sports and Recreation in Bogotá, the Health Department of the city of Bogotá, DADEP, and UniAndes.

**Analysis:** We will use mixed methods to assess the longitudinal impact of the Ciclovía/Recreovía on physical activity levels among adults and children. For qualitative methods, we will use the citizen scientist *Nuestra Voz* (Our Voice) model that employs a tablet-based application to empower residents to document features of their neighborhoods that promote and hinder physical activity. Drs. [name], [name], and [name] have successfully used this approach in diverse communities including with Latinos in the US and in Latin America. For quantitative methods, we will assess the median differences in moderate to vigorous PA (pre-post) and interquartile range (IQR) of the self-reported and objectively measured (via accelerometers) PA outcomes, which will be compared using the Wilcoxon Signed Rank Test.

## **B.7. Aim 4: Develop Center Research Plans**

**B.7.1. Needs assessment.** We will conduct a needs assessment in the first 3 months of the project period with the goal of identifying the needs and assets related to NCD prevention and PA promotion among the Collaboratory partnership and the communities that they serve. The methods for the needs assessment are described in the **Coordinating Unit description in section B.5**. These results will help to assess research plans, priorities and opportunities for the Center and its expansion in the Latin American region.

**B.7.2. Finalize plans.** To finalize short-, mid-, and long-term goals, the S-C will utilize principles of CBPR (see **Planning Unit description-Table 1** for proposed goals). We will engage two stakeholder groups to gather input on research and education priorities for the partnership. Stakeholder groups will include participants in pilot studies, multi-sectoral colleagues from the Steering Committee, and other groups as needed. The investigative team will meet with stakeholders to strategize and finalize short-, mid-, and long-term goals.

## **B.8. Sustainability and Future Directions**

The ultimate goal of the activities planned during this 2-year period are to create, enhance, and support the infrastructure and capacities that are needed to maintain a sustained effort focused on NCD prevention in Colombia and the Latin American region. This project is built on an existing partnership that has already successfully maintained collaborations and will expand to engage additional partners from diverse sectors, thus promoting sustainability. The partnership development activities will promote sustained engagement in research activities. Research enhancement activities, including scholar exchanges and various training programs, are designed not only to sustain research activities, but also to expand and grow these activities over time and throughout the Latin American region. Finally, the pilot projects are aimed at producing the necessary preliminary experience and evidence to support future larger scale projects. As described in **Table 1** of the **Planning Unit** description, short- and mid-term goals include submitting proposals for larger-scale studies that build on findings from the pilot studies.

## A. Specific Aims (Coordinating Unit)

The Stanford-Colombia Collaboratory on Chronic Disease (S-C) will focus on prevention of major non-communicable diseases (NCDs) facing Colombia and the Latin American region, including cancer, cardiovascular disease, diabetes, and depression. NCDs are responsible the largest proportion of deaths in Latin America (69%) and in Colombia specifically (71%). Prevention will focus on promotion of physical activity given that inactivity is one of the most important contributors to the global burden of NCDs, responsible for ~6-10% of major NCDs worldwide. In Colombia, 47% of adults and 74% of adolescents do not meet physical activity recommendations. Essential to effectively controlling the NCD epidemic in low- and middle-income countries (LMICs) in Latin America, such as Colombia, is to increase research capacity in the areas of theory-based behavioral intervention research, statistical methods to assess impact and potential for dissemination, and strategies for effectively engaging community members and key stakeholders. The S-C includes a systematic and coordinated plan to support such research capacity building activities.

S-C is built upon an existing strong partnership between Stanford University School of Medicine and the Universidad de los Andes (UniAndes) in Bogotá, Colombia and is the result of regional think tanks focused on behavioral change and PA interventions, first held in Bogotá in 2011 and again in 2016 at Stanford. The research plans are informed by a socio-ecological model for health promotion and guided by principles of Community-Based Participatory Research (CBPR). These frameworks will also guide the Coordinating Unit.

The **S-C Coordinating Unit's function** will be to provide seamless administrative support to facilitate day-to-day operations of the S-C, including the two proposed pilot studies, all three cores, all communications internal to the study and external to the study (e.g., with granting agencies, outside collaborators, and outside investigators who express interest in using the cores), oversight of the database and data management system, financial and grants management, and regulatory requirements, such as IRB approvals and annual progress reports.

The Specific Aims of the Coordinating Unit are to:

1. **Provide administrative support to facilitate the conduct of the two proposed pilot studies**, including the clinic-based intervention to integrate physical activity prescription and practice into the clinical care of breast cancer survivors and the community-based intervention focused on initial evaluations of Ciclovias and Recreovias in Bogotá.
2. **Provide administrative support for the proposed training and research enhancement activities**, including a scholar exchange program between Stanford and the Universidad de los Andes (UniAndes), a professional certification program in behavioral sciences for health, development of the Master's Program in in Epidemiology, and the specialized seminars.
3. **Provide administrative support for the three proposed cores:** 1) Data Management and Statistical Analysis, 2) Development and Evaluation of Theory-Based Behavioral Interventions, and 3) Community Engagement and Translation.

The partnership between Stanford University and UniAndes is uniquely positioned to provide seamless and unified coordination given their existing successful collaborations that include scholar exchanges, regional think tank workshops, and joint research projects. The investigative teams at both Stanford and UniAndes have extensive experience conducting large-scale and complex research projects, including international collaborations. Detailed plans and milestones, developed and executed as part of the proposed S-C, will provide a foundation to monitor and track progress, identify barriers and solutions, and strategically plan for the future.

## B. Research Strategy – Coordinating Unit

The Coordinating Unit will be located at UniAndes. This Unit will provide all administrative services and support to facilitate the completion of the research and capacity building goals. This unit will be directed by [name] [name], a renowned researcher in the field of physical activity (PA) in Colombia, with local participation of [name], a well-respected behavioral scientist/psychologist with expertise in the behavioral theories and interventions related to behavior change in promoting physical activity and experience in the assessment of mental health issues. UniAndes has the capability of serving as the home institution for the planned collaboration. Established in 1948, UniAndes is a private non-profit organization with approximately 18,000 students and more than 640 full-time faculty in 12 Schools. UniAndes offers 39 undergraduate programs, 15 doctoral, and 55 master level programs. UniAndes has been ranked consistently among Latin America's Top 10 Universities according to QS World University Rankings. In 2016, it was ranked eighth in the region. Furthermore, UniAndes has extensive experience in international collaborations and the administration of grants with international funding. For example, it has received funding by the World Bank, USAID, and the European Commission. At Stanford, Drs. [name], [name], and [name] will play collaborating/consulting roles in this Unit. Their relevant expertise is summarized in the Overall Plan and Bio Sketches sections of the current application.

